15.15 Dosage modifications

The IMP will be administered as a single bolus dose based on the participant's weight, and no further dose modifications are required in patients with co-morbid conditions (e.g. renal or liver dysfunction) or concomitant therapies.

If the patient experiences an adverse toxicity reaction to the IMP, whilst the single bolus dose is being administered, administration of the IMP will be stopped and no further IMP will be administered. Any dose reductions or delays occurring for other reasons (e.g. problems with intravenous access, etc.) will clearly be documented on the CRF.

There are no rescue medications in the event of toxicity reactions. Treatment will consist of general supportive measures.

Experience of acute overdose with Artesunate is limited. A case has been documented in a 5-yearold child who was inadvertently administered rectal Artesunate at a dose of 88 mg/kg/day over 4 days, representing a dose more than 7-fold higher than the highest recommended Artesunate dose (Campos *et al.*, 2008). The overdose was associated with pancytopenia, melena, seizures, multiorgan failure and death. Treatment of overdose should consist of general supportive measures.

15.16 Known drug reactions and interaction with other therapies

Artesunate is rapidly and extensively converted to dihydroartemisinin (DHA), the active metabolite, primarily by plasma and erythrocyte esterases. DHA elimination is also rapid (half-life approximately 45 min) and the potential for drug-drug interactions appears limited. In vitro drug-interaction studies have demonstrated minimal effects of artesunate on cytochrome P450 isoenzymes. Few clinical drug-drug interaction studies have been performed, however no clinically significant interactions have been identified (See Investigators Brochure, Version 1.0, Dated 6th January 2016).

There are no prohibited concomitant medications or therapies. Contraindications include:

- Serious adverse reaction or hypersensitivity to artesunate or any other artemisinin.
- Pregnancy due to the risk of spontaneous abortion, especially during the first trimester.

15.17 Prior and Concomitant medication

There are no restrictions on prior therapies taken by a subject and concomitant therapies and they are permitted concurrently with the trial medication. Investigational drugs, devices, procedures or therapies (other than the trial medication) will not be used during the subject's participation in the study because of their potential to confound the results. Enrollment into a strictly observational trial is permitted, as long as the study assessments in this trial are not compromised.

Prior therapies taken by a subject and concomitant therapies subject receives for the first 48-hours will be captured in the CRF.

15.18 Trial restrictions

There are no trial restrictions.

15.19 Assessment of compliance

There is no compliance measurement requirement for this trial. The IMP is administered as a single dose by qualified clinically trained research fellows at the hospital.

15.20 Name and description of each Non-Investigational Medicinal Product (NIMP)

N/A

15.21 Arrangements for post-trial access to IMP and care

There are no arrangements for post-trial provisions after completion of the trial.

17 Pharmacovigilance

17.1 General Definitions

Term	Definition				
Adverse Event (AE)	Any untoward medical occurrence in a participant to whom a medicinal				
	product has been administered, including occurrences which are not necessarily caused by or related to that product				
Adverse Reaction (AR)	An untoward and unintended response in a participant to an investigational medicinal product which is related to any dose administered to that participant. The phrase "response to an investigational medicinal product" means that a causal relationship between a trial medication and an AE is at least a reasonable possibility, i.e. the relationship cannot be ruled out. All cases judged by either the reporting medically qualified professional or the Sponsor as having a reasonable suspected causal relationship to the trial medication qualify as adverse reactions.				
Serious Adverse Event (SAE)	 A serious adverse event is any untoward medical occurrence that: Results in death. Is life-threatening. Requires inpatient hospitalisation or prolongation of existing hospitalisation Results in persistent or significant disability/incapacity. Consists of a congenital anomaly or birth defect. Other 'important medical events' may also be considered serious if they jeopardise the participant or require an intervention to prevent one of the above consequences. NOTE: The term "life-threatening" in the definition of "serious" refers to an event in which the participant was at risk of death at the time of the event; it does not refer to an event which hypothetically might have caused death if it were more severe. 				
Serious Adverse Reaction (SAR)	An adverse event that is both serious and, judged by either the reporting investigator or the Sponsor as having a reasonable causal relationship to a medicinal product.				
Suspected Unexpected Serious Adverse Reaction (SUSAR)	 A serious adverse reaction, the nature and severity of which is not consistent with the information about the medicinal product in question set out in the Reference Safety Information (RSI): In the case of a product with a marketing authorisation, in the summary of product characteristics (SmPC) for that product. In the case of any other investigational medicinal product, in the investigator's brochure (IB) relating to the trial in question. 				

17.2 Site Investigators Assessment

The Principal Investigator is responsible for the care of the participant, or in his/her absence an authorised medic within the research team is responsible for assessment of any event for:

- Seriousness Assessing whether the event is serious according to the definitions given in section 17.1.
- Causality

Assessing the causality of all serious adverse events/reactions in relation to the trial treatment according to the definition given. If the SAE is assessed as having a reasonable causal relationship, then it is defined as a SAR.

• Expectedness

Assessing the expectedness of all SARs according to the definition given. If the SAR is unexpected, then it is a SUSAR.

• Severity

Assessing the severity of the event according to the following terms and assessments. The intensity of an event should not be confused with the term "serious" which is a regulatory definition based on patient/event outcome criteria.

- Mild: Some discomfort noted but without disruption of daily life
- Moderate: Discomfort enough to affect/reduce normal activity
- Severe: Complete inability to perform daily activities and lead a normal life

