9.2 Assessment and management of risk

Artesunate has been extensively used in the treatment of both child and adult malaria including use in critically ill patients. They are very well tolerated, with a well-documented safety profile (see

previous section). As patients will receive all other clinically indicated treatments, there is no risk of ineffective therapy by administration of the trial treatment.

Whilst there is a risk of adverse events occurring as a result of oral or intravenous Artesunate, including gastrointestinal symptoms, neutropenia, reticulocytopenia, liver enzyme disturbance, bradycardia and prolonged QT intervals (Riberio & Olliaro 1998), these risks are low (all occurring in under 1.5% of recipients) and unlikely to result in significant detriment to the subject particularly in light of the serious nature of their injuries. Moreover, anaphylactic reactions to Artesunate are extremely rare.

The potential benefits of Artesunate in reducing multiple organ failure outweigh the risk of adverse events associated with the medication. Artesunate will be administered as an intravenous preparation due to the critical illness of the subjects enrolled that will preclude oral administration. Intravenous Artesunate has been more widely studied within the literature compared to intramuscular Artesunate (Jones *et al.* 2007) and is therefore the preferred route of administration in this trial.

This trial is categorised as: Phase 2a

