13.3.6 Participants lacking capacity

Most, but potentially not all, subjects will be incapacitated at the time of eligibility (critical injury, mechanical ventilation, sedation), such that the Mental Capacity Act (England; 2005) and Declaration of Helsinki (World Medical Association; 2013) provide guidance. Patients will be enrolled within four hours of their injury and within two hours of admission to the accident and emergency department. This is a particularly stressful time for relatives and families, an important consideration when the intervention under investigation is time sensitive. This study requires the IMP to be given rapidly, thereby necessitating that eligible patients are consented very soon after hospital admission. As injury is an unexpected event, it is uncommon for relatives to be present at the time of hospital admission.

As stipulated by GCP the subject and/or their Personal LR (e.g. next of kin) should be given ample time to consider giving their consent for the study. It is felt that 24 hours is sufficient time for the patient and/or Personal LR to consider participation and give informed consent. However, the need for urgent treatment in this trial means implementation of the research cannot be delayed and it would be inappropriate to delay treatment until fully informed consent can be obtained from the patient or other nominated representative. Patients incapable of giving consent in emergency situations are an established exception to the general rule of informed consent in clinical trials.

As the timeframe required for subject or Personal LR consent is not compatible with the time sensitivity of this trial, several approaches to obtaining informed consent will be used. All are consistent with the Mental Capacity Act (England; 2005) and Declaration of Helsinki (2013).

Consent for initial enrolment in the trial will be sought from a Professional LR in the form of independent clinicians (trauma lead for the subject), who are familiar with the consenting process and present at every trauma call.

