19.9 Interim analysis and criteria for the premature termination of the trial

An interim analysis will be performed after recruitment of the first 52 patients. The analysis will be limited to an analysis of safety data between the two groups. Provided there are no issues regarding safety or toxicity, the study will be continued with an increased dose in the intervention arm.

At the interim analysis, a qualitative assessment of all recorded AEs and SAEs will be undertaken by the DMC to determine if the trial should be discontinued on account of safety concerns. AEs will be coded by system organ class (SOC) and preferred term (PT), using MedDRA. An overview of all AEs, SAEs, relationship to IMP, intensity and AEs leading to withdrawals or death will be presented by treatment group. AEs will be summarised using descriptive statistics. Treatment emergent AEs will be analysed separately.

The number and percentage of subjects with abnormal vital signs and/or laboratory values will be presented by treatment group. The data may also be presented as shift tables (normal, abnormal and not clinically significant, abnormal and clinically significant) with screening values as a reference.

The trial will be terminated following the interim analysis based on the safety data. The criteria for termination (e.g. total SAEs per group) shall be defined by the DMC. Outside the planned interim analysis the study will be terminated only on the grounds of new safety concerns or unforeseen recruitment issues.

The sponsor retains the right to stop the study, should the need arise.

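### The only AE intensity scale (17.2) rests on discomfort and daily activity, so it grades incapacitated patients and laboratory events poorly and weakens the intensity column of the safety tables

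*Protocol*

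**What the plan says.** Section 17.2 has an authorised medic assess any event for seriousness, causality, expectedness and severity. The severity instruction is "Assessing the severity of the event according to the following terms and assessments", and three grades follow:

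- The lowest grade is "Mild: Some discomfort noted but without disruption of daily life".
- The middle grade is for discomfort that limits what the patient would ordinarily do.
- The top grade is "Severe: Complete inability to perform daily activities and lead a normal life".

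There is no second scale, no rule for patients who cannot report symptoms or perform activities, and no grading of laboratory values.

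On the population, 13.3.6 states: "Most, but potentially not all, subjects will be incapacitated at the time of eligibility (critical injury, mechanical ventilation, sedation". On the expected risks of artesunate, 9.2 names gastrointestinal symptoms first and then "neutropenia, reticulocytopenia, liver enzyme disturbance, bradycardia and prolonged QT intervals".

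On use, 19.9 says of the interim safety review: "An overview of all AEs, SAEs, relationship to IMP, intensity and AEs leading to withdrawals or death will be presented by treatment group". Section 19.3 has the safety data re-analysed on the final cohort in the same way. AE reporting runs from dosing to 28 days (17.6).

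**The concern.** The scale suits ambulatory patients who can say how they feel and whose daily life can be disrupted. Here most subjects enter the trial critically injured, ventilated or sedated. Read one way, such a patient meets the top grade before any event occurs. Read the other way, an event that causes no reportable discomfort falls to the bottom grade or has no grade. The protocol does not say which reading applies.

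The intensity column is among the summaries the DMC sees before the trial moves from 2.4 to 4.8 mg/kg. If the grade depends on the patient's injury state or on which reading the assessor takes, a real difference in depth of toxicity between arms is harder to see in that column. The cost is lost contrast, not a shift in favour of one arm: allocation is randomised, and 13.6 keeps those collecting follow-up blinded.

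**Working it through.** No figure in the protocol is at issue, so there is none to reproduce. The check sets the passages side by side and then illustrates the size.

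**1. Fit to the named risks.** Section 9.2 lists six.

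| Risk in 9.2 | How it is detected | Threshold in the 17.2 scale |
|---|---|---|
| Gastrointestinal symptoms | patient report | yes, if awake |
| Neutropenia | laboratory | none |
| Reticulocytopenia | laboratory | none |
| Liver enzyme disturbance | laboratory | none |
| Bradycardia | monitor | none |
| Prolonged QT | ECG | none |

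Five of the six have no usable threshold.

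**2. One event, two readings.** Take a low neutrophil count in a sedated, ventilated patient.

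- Reading A, the patient's state: daily activities are impossible, so the event is Severe.
- Reading B, the effect of the event itself: no discomfort can be noted, so it is Mild or cannot be graded.

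Two assessors can both follow 17.2 and differ by two grades, and the neutrophil count plays no part in either answer. Reading A compresses the scale at the top. Reading B leaves laboratory events at the bottom or ungraded. These are alternatives and cannot both describe the same patient, so what the text shows is ambiguity.

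**3. Size under Reading A, as an illustration.** Assume that every patient has at least one event and is counted by worst grade, and that a share m, equal in both arms, is graded Severe because of baseline state. With true severe proportions p₀ (placebo) and p₁ (active):

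- observed proportion: qᵢ = m + (1 − m)pᵢ
- observed difference: q₁ − q₀ = (1 − m)(p₁ − p₀)

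The arm sizes are the interim ones from 11.6: 17 placebo and 35 low dose. Approximate power at two-sided 5% is Φ[(|q₁ − q₀| − 1.96·SE₀)/SE₁], with SE₀ pooled and SE₁ unpooled.

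For p₀ = 10% and p₁ = 40% at m = 0.5: q₀ = 0.5 + 0.5 × 0.10 = 0.55, q₁ = 0.5 + 0.5 × 0.40 = 0.70, difference 0.15, power 19%.

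| m | Difference, 10% vs 40% | Power | Difference, 10% vs 30% | Power |
|---|---|---|---|---|
| 0 | 30 points | 62% | 20 points | 33% |
| 0.25 | 22.5 | 32% | 15 | 17% |
| 0.5 | 15 | 19% | 10 | 10% |
| 0.75 | 7.5 | 11% | 5 | 7% |
| 0.9 | 3 | 7% | 2 | 5% |
| 1 | 0 | – | 0 | – |

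The protocol gives neither m nor the severe proportions, so all of these are assumptions. No test of intensity is planned, and power serves here only as a gauge of how visible a difference would be. The normal approximation is rough near m = 0.9.

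**4. What else the DMC sees.** Under 19.9 it also receives AEs by system organ class and preferred term, SAEs, relationship to IMP, AEs leading to withdrawal or death, and the number and percentage of subjects with abnormal vital signs or laboratory values. Shift tables are optional and only split abnormal values by clinical significance. None of these displays shows how deep an abnormality is.

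**The case against.** The strongest reply has four parts.

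- **The scale grades the event, not the patient.** A sensible medic would not call a trivial rash Severe because the patient is ventilated. That is a fair reading, and 17.2 does not force the other. But the text does not settle it, and the sensible reading still leaves laboratory findings without a threshold.
- **Incapacity is described at eligibility only.** The AE window runs to day 28, and 13.3.6 provides for patients who regain capacity. This stands. The difficulty is greatest early and eases as patients recover, and no percentage is given.
- **Laboratory toxicity has its own route to the DMC.** This also stands. Abnormal values are shown by arm whatever the intensity grade, and 13.8.3 collects the safety panel daily on days 1–7 and then around days 14, 21 and 27 while the patient is in hospital. The limit is that the display is abnormal versus normal.
- **The decision does not rest on intensity.** Section 19.9 describes a qualitative review of all AEs and SAEs, and its only example of a stopping criterion is total SAEs per group. This stands too.

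A reader might go further and infer that the intensity table is uninformative, that greater toxicity on artesunate would go unseen, or that every risk in 9.2 lies outside the scale. The documents support none of these. The table is empty of contrast only at m = 1, the other displays bypass the scale, and 9.2 includes gastrointestinal symptoms, which an awake patient can report.

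**Conclusion.** The point holds as a matter of fit. The protocol itself fixes this scale, so it is not a detail left to the SAP. The scale suits incapacitated critical-care patients poorly and gives no threshold for five of the six risks in 9.2. The intensity column in the interim and final safety tables will therefore discriminate poorly and partly reflect injury state.

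The size cannot be fixed from the documents. The loss of contrast is the factor 1 − m under the patient-state reading, with m unknown. Even with no such loss, 17 versus 35 patients gives only 33% to 62% power for the assumed differences of 20 and 30 points, so the column was never going to carry the decision alone. This is a worthwhile, inexpensive improvement to one safety summary. It does not undermine the interim review or the safety endpoint, which is the SAE rate to day 28 (11.3.2).

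**What to change.** Replace the 17.2 scale by amendment before the interim review:

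1. **Laboratory AEs:** grade with a published toxicity table, derived by program for analytes already collected under 13.8.3, such as neutrophils, ALT, AST and bilirubin. Reticulocytes are not in that panel and no ECG appears in the schedule, so reticulocytopenia and QT prolongation cannot be graded from the planned data. The amendment should say so.
2. **Clinical AEs:** grade by the consequence attributable to the event, relative to the patient's state just before it. For example: no change in care; added treatment or monitoring; major escalation beyond what the injury already required. State that this rule applies to incapacitated patients. Keep the wording distinct from the seriousness criteria in 17.1, and do not use threat to life as a grade.
3. **Tables:** use the same scale at the interim and final analyses, and regrade any AE already recorded on the old one.

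Laboratory grades will still reflect haemorrhage and injury in both arms. The gain is that depth can be compared against randomised placebo. The cost is amendment wording, CRF options, brief training and slightly longer AE forms. Sample size, randomisation and efficacy analyses do not change.

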17.3 Reference Safety information

IB (Version 1.0, Section 6.10, Dated 6th January 2016)

17.4 Notification and reporting Adverse Events or Reactions

If the AE is not defined as SERIOUS, the AE is recorded in the study file and the participant is followed-up by the research team.

Death as a result of disease progression and other events that are primary or secondary outcome measures are often not considered to be SAEs and can be reported in the normal way on the CRF.

17.5 Notification of AEs of special interest

N/A

17.6 Adverse events that do not require reporting

The period for AE reporting is from dose administration to 28 days. The following SAEs are clinical outcome measures and are expected due to the nature of the injuries sustained:

- Deaths
- Infection
- Organ failure (single or multi-)
- Acute lung injury
- Acute kidney injury

The following SAEs are not clinical outcome measures but are expected SAEs due to the nature of injuries sustained:

- Thromboembolic events (deep vein thrombosis, pulmonary embolism)
- Ischaemic events (myocardial infarction, stroke, transient ischaemic attack)
- New-onset major bleeding

New onset major bleeding refers to a second episode of major bleeding which is temporally and clinically separate from the major haemorrhage that led to the entry of the participant into this study.

Any event meeting the definition of an SAE and not listed above will be treated as an 'unexpected SAE' and will require notification as outlined in Section 17.7.

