11.6 Trial Design

This is a single-centre, randomized, placebo-controlled, parallel group study with a sequential groupdosing regimen (adaptive design). Its aim is to evaluate the safety and efficacy of Artesunate treatment compared to placebo, in addition to standard treatment, in severely injured trauma patients with traumatic hemorrhage. All subjects will be managed in accordance with local guidelines for traumatic hemorrhage.

Subjects will be assessed for eligibility upon arrival to the hospital. Due to the urgent/emergency nature of the intervention subjects will be recruited within 4 hours of their injury and within 2 hours of admission to the accident and emergency department. Eligible patients therefore need to be consented very soon after admission. As most, but potentially not all, subjects will be incapacitated at time of eligibility, consent can be obtained from relatives or if no relatives are present two

doctors (one independent of the trial) will decide on consent. If and when the subject regains physical and mental capacity they will be provided written information on the trial and will be given the opportunity to ask questions, informed consent will be sought for continuation in the trial. For any subject included but did not regain full capacity, consent will be sought from a relative or other appropriate representative for continuation in the trial.

Subjects will be randomized to one of three groups:

- Placebo arm (n = 35)
- Low Dose intervention arm: active drug 2.4mg/kg (n=35)
- High Dose intervention arm: active drug 4.8mg/kg (n=35)

The trial will be divided into two stages. The first stage will enroll patients into the Placebo (n=17) and Low Dose intervention arms (n=35), following which an interim analysis will be performed. The analysis will be limited to an analysis of safety data between the two groups. Provided there are no issues regarding safety or toxicity, the study will continue with the second phase enrolling patients into the high dose intervention arm (n=35) or placebo (n=18).

Each subject will be dosed and then remain in the study for 28 days or until they are discharged. There will be a 90-day follow-up though this will be conducted using data obtained via the NHS spine services (Health and Social Care Information Centre).

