Subjects who do not complete the primary outcome end-point at 48-hours (e.g. due to death or discharge) will be replaced. Variables will be evaluated at different time points from screening through day 28 as per the schedule of events.

Adverse events (AEs) and serious adverse events (SAEs) will be reviewed by the trauma research fellow (who is a clinician) on a daily basis from the point of dosing throughout the 28-day subject participation in the trial. Please see Section 17 for further details.

The following will be determined at various points throughout the trial SOFA score, renal injury, lung injury, infection rate, the number of mechanical ventilation days, RRT days, vasopressor days, CTCOFR score, ACCU length of stay and the hospital length of stay.

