- Total length of critical care stay.
- Total length of hospital stay.

Day 8 to Day 14:

- Monitor AEs and record SAEs.
- Record safety blood results (day 14 +/- 1).
- Renal injury, as per the RIFLE score.
- Lung injury as per the Berlin definition.
- Infection rate.
- Number of ventilation free days.
- RRT days.
- Vasopressors days.
- CTCOFR score.
- Total length of critical care stay.
- Total length of hospital stay.

Day 15 to Day 28:

- Monitor AEs and record SAEs.
- Record safety blood results (day 27 +/- 1)
- Renal injury, as per the RIFLE score.
- Lung injury as per the Berlin definition.
- Infection rate.
- Number of ventilation free days.
- Total length of critical care stay.
- Total length of hospital stay.
- Mortality status.

Until discharge:

- Number of ventilation free days.
- Total length of critical care stay.
- Total length of hospital stay.
- Mortality status.

Day 90 (Follow-up):

• Mortality status.

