The total 60 mls of blood sampled equates to approximately 1% of the total circulating blood volume over the 12-hour period. As recruited patients will be receiving blood transfusions as part of their standard clinical care during this time, it is not anticipated that the samples taken will have any

adverse effects on clinical outcomes. Blood that is collected and not used for PK/PD analysis will be processed and stored for use in ancillary research (See Section 13.3.9)

Clinical Blood Sampling

In order to calculate SOFA and RIFLE scores, ascertain presence of infection, and degree of shock on admission, record will be made the following parameters as part of routine clinical bloods (i.e. no additional specific research blood draws will be taken):

- Platelets
- Creatinine
- Estimated Glomerular Filtration rate (eGFR)
- Bilirubin
- Total white blood cells
- Neutrophils
- Lymphocytes
- C-reactive protein
- Arterial or venous blood gas result (admission result only)

In addition, in order to ensure adequate safety of the IMP, the following will be monitored and for the purposes of safety monitoring for AEs and SAEs:

- Haemoglobin
- Haemocrit
- Red cell count
- Mean cell volume
- Mean corpulscular haemoglobin (MCH)
- Red blood cell distribution width (RDW)
- Mean corpuscular haemoglobin concentration (MCHC)
- White cell count
- Platelet count
- Neutrophils
- Lymphocytes
- Monocytes
- Eosinophils
- Basophils
- Alanine aminotransferase (ALT)
- Aspartate aminotransferase (AST)
- Alkaline phosphate
- Gamma-glutanyl transpeptidase (GGT),
- Bilirubin
- Creatinine
- Urea
- Sodium
- Potassium
- Calcium
- Albumin
- Prothrombin Time
- International Normalised Ratio (INR)

These parameters will be collected daily for days 1-7, and subsequently on day 14±1, day 21±1, and day 27±1, provided the subject is still in hospital. Where possible, these data will be collected from

routine clinical bloods. In the event they have not been undertaken as part of routine clinical bloods, the research fellow will take the bloods at the specified times (unless the subject declines).

Radiological Investigation Results

Radiological investigations (including Chest X-rays and CT scans) undertaken as part of a subjects' clinical course, will be examined for calculation of ARDS scores as well as for assessment of adverse events. No specific radiological investigations will be undertaken for research purposes.

Outcome Measures

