13.8.4 Follow-up Procedures

There are no specific follow-up procedures for subjects once they have been discharged or completed the 28-day trial period. Trauma Research Fellows will collect study information including AEs and SAEs by as per the Schedule of Assessment (Section 13.8.2).

In order to ensure completion of follow-up for SAEs for subjects who are discharged from hospital prior to 28 days, an investigator will attempt to contact the subject or their General Practitioner by telephone on or around 28 days to encourage reporting of any SAEs occurring following discharge. Subjects will be provided with details of whom to contact if they have any questions regarding the trial or wish to provide further information.

Study patient 90-day mortality follow-up shall be conducted using data obtained via the NHS spine services (Health and Social Care Information Centre). It is not practicable to attempt to approach subjects to request "their" survival data; such actions are precluded because there is sufficient potential to do harm and cause distress by inadvertently approaching the families of deceased study subjects.

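### Non-serious AEs and safety bloods have a stated window to Day 28, but the procedures observe them only until discharge or death, so raw counts by arm can favour the arm that leaves observation sooner

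*Protocol*

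**What the plan says.** The protocol gives two accounts of how long AEs are collected.

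**To Day 28 for everyone.** Section 17.6: "The period for AE reporting is from dose administration to 28 days". Section 11.6 has AEs and SAEs reviewed "on a daily basis from the point of dosing throughout the 28-day subject participation in the trial". In Section 13.8.1 the blocks from 49 hours to Day 28 carry the instruction "Monitor AEs and record SAEs" with no condition that the subject is an inpatient. The table in Section 13.8.2 agrees.

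**To discharge.** Section 11.6 also says: "Each subject will be dosed and then remain in the study for 28 days or until they are discharged". After daily panels on Days 1-7, Section 13.8.3 schedules safety bloods on "day 14±1, day 21±1, and day 27±1, provided the subject is still in hospital". Section 13.8.4 provides no specific procedure after discharge except one attempted telephone contact with the subject or GP at about Day 28, "to encourage reporting of any SAEs occurring following discharge".

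**Analysis.** Section 19.9 summarises AEs descriptively by group and adds: "The number and percentage of subjects with abnormal vital signs and/or laboratory values will be presented by treatment group". It mentions no time at risk. The DMC reviews these data at the interim analysis, before the dose is increased, and Section 19.3 repeats the same safety analysis at the end. The named safety endpoint in Section 11.3.2 is the SAE rate in the first 28 days. Length of hospital stay and mortality are secondary endpoints.

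**The concern.** A 28-day window is promised, but for non-serious AEs no step is described by which a discharged subject could be asked about them, and the bloods stop at discharge. The observed window then ends at discharge or death. Both occur after randomisation, and both are endpoints that treatment may change.

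If one arm goes home sooner, it has fewer days in which a non-serious AE can be noted, and somewhat fewer blood panels. Its raw counts and percentages fall even when toxicity is the same. Earlier death has the same effect. At stake is how the non-serious AE and laboratory tables are read, both at the dose-escalation review and in the final safety summary.

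**Working it through.** The protocol gives no expected AE rate or observation time, so it has no figure of its own to reproduce on this point. The size is shown as a range under stated assumptions.

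**Inputs from the protocol**
- Window: 28 days (Section 17.6).
- Scheduled blood panels: Days 1-7, 14, 21 and 27, which makes 10 (Section 13.8.3).
- Hospital stays: 25 v 15 days (Section 9.1). This contrasts patients needing at least four red-cell units with others, not treatment arms.

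**Assumptions, not in the protocol**
- Stays of 20 v 25 or 15 v 25 days, either fixed or log-normal with those medians and log-SD 0.8, capped at 28 days.
- The same AE hazard in both arms, either constant or declining with a half-life h of 10 or 5 days.
- Non-serious AEs seen only up to discharge.

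**Formula.** Expected AEs seen by day t are proportional to H(t) = t for a constant hazard, and to H(t) = 1 - 2^(-t/h) for a declining one. The count ratio is H(shorter stay) / H(longer stay). It would be 1.00 with a common window.

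**Fixed stays**
- Constant hazard: 20/25 = 0.80; 15/25 = 0.60.
- h = 10: 0.750/0.823 = 0.91; 0.646/0.823 = 0.79.
- h = 5: 0.9375/0.969 = 0.97; 0.875/0.969 = 0.90.

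**Log-normal stays (simulated)**
- Constant hazard: mean days observed 19.16/21.20 = 0.90; 16.27/21.20 = 0.77.
- h = 10: 0.94; 0.85.
- h = 5: 0.96; 0.90.

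The deficit is thus about 3-20% for 20 v 25 days and 10-40% for 15 v 25 days. At the largest value for 20 v 25, a true AE rate ratio of 1/0.80 = 1.25 would appear as 1.00.

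**Percentage with at least one AE.** Take a constant hazard that would give 60% over a full 28 days, with log-normal stays. The observed percentage is 48% for a median stay of 25 days, 45% for 20 and 39% for 15.

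**Blood panels.** Panels falling on or before discharge number 7 for a 10-day stay, 8 for 15 or 20 days, 9 for 25 and 10 for 28. The laboratory effect is small because 7 of the 10 panels fall on Days 1-7.

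**Would rates per inpatient day cure this?** The rate ratio is the count ratio times (longer stay / shorter stay), for fixed stays:
- Constant hazard: 0.80 x 25/20 = 1.00, so the cure works.
- h = 10, 20 v 25: 0.911 x 1.25 = 1.14.
- h = 5, 20 v 25: 0.968 x 1.25 = 1.21.
- h = 5, 15 v 25: 0.903 x 25/15 = 1.50, when the truth is 1.00.

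With a declining hazard the rate is biased against the shorter-stay arm, here by more than the raw count was biased in its favour.

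**The case against.** The strongest reply is that the protocol does commit to 28 days. Section 11.6 speaks of 28-day participation, the schedule runs AE monitoring to Day 28 without an inpatient condition, Section 13.8.4 has the fellows collect AEs as per that schedule, and Section 13.9 follows even withdrawn subjects who were dosed to Day 28. A reader might infer from the other sentence in Section 11.6 that participation ends at discharge. The documents do not support that as settled, because it is one of two conflicting statements. What stands is that no described procedure would bring in a non-serious AE after discharge.

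A reader might also infer that the safety endpoint is biased in the same way. It is not: SAEs have a fixed 28-day window and are sought after discharge. The weakness there is only that ascertainment rests on one attempted contact.

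Section 19.9 describes a qualitative DMC review with descriptive summaries, and detail on exposure may properly be left to the SAP. That is fair as to methods. But the collection window is a protocol instruction, and no SAP can recover events that nobody asked about.

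Finally, the drug is a single bolus with short half-lives (Section 9.1), and the one dose-related effect cited, a fall in reticulocytes, appeared at four days (same section). A hazard that declines early is therefore plausible, which points to the lower end of the ranges. This stands.

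**Conclusion.** The point holds for non-serious AEs and laboratory abnormalities, and only for those. The passages on the AE window conflict, and the procedures as written observe these events until discharge or death, so raw numbers and percentages by arm can favour whichever arm leaves observation sooner.

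With equal toxicity the deficit in non-serious AEs is about 3-20% for 20 v 25 days. It is 10-40% for 15 v 25 days, which is an upper illustration: those stays separate transfusion groups, and nothing in the protocol suggests that the arms would differ by 10 days. With a 5-day half-life the deficits are about 3-4% and 10%. The laboratory part is small. All sizes rest on assumed stays and hazards.

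A reader might conclude that artesunate will look safer than it is. The documents do not fix the direction: shorter stay or earlier death reduces an arm's observed events, whereas a drug that prevents deaths could lengthen observation and raise them. This is a cheap improvement, not a flaw in the named safety endpoint.

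**What to change.** 1. Reconcile Sections 11.6 (both statements), 13.8.3, 13.8.4 and 17.6, with the schedule in 13.8.1 and 13.8.2, to one AE collection window. Either ask about non-serious AEs at the existing Day-28 contact, or state that non-serious AEs and safety bloods are collected from inpatients only. Keep SAEs to Day 28 in all subjects.
2. In Section 19.9, present non-serious AEs and laboratory abnormalities by arm within a fixed early window, Days 1-7, beside the counts to Day 28. Give days observed and the number of subjects reached at Day 28, by arm. The early window reduces the bias but does not remove it, since some subjects die or go home before Day 7.
3. Use rates per inpatient day as a supplement at most, for the reason shown in the working.

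The cost is one extra question or a change of wording, and one additional table. Days observed can be derived from the stay and mortality data already collected.
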